5.9 Cost/Compensation to Participants

There are no anticipated costs to the patient. Wound debridement procedure is reimbursed by CMS under CPT code 11042. The micro water jet device and disposable accessories are provided by Medaxis AG as part of the study. We do not anticipate any possible injury to the patient or other liability that could accrue to the patient under the normal process of care. Participant will be paid \$50 total for participating in the study.

6.0 SAFETY

6.1 General Protection

Wound care instructions will be reviewed at every visit to ensure patient compliance with the study protocol. Patients will be instructed to inspect the wound at each dressing change and on how to detect signs of wound deterioration, and to immediately report these signs to the investigator. If the ulcer worsens, medical treatment as needed, will be initiated by the investigators. At each visit the patient will be questioned about potential adverse experiences with the response recorded in patient's chart. This includes exacerbation of existing condition or event. Infection of soft tissue or bone, amputation, need for incision and drainage, iatrogenic ulcer formation, or deterioration of the wound will be considered as an adverse event. The patient will also be questioned as to any problems, adverse experiences, or digressions from the study procedures and restrictions. Relevant findings will be noted in the patient's chart.

6.2 Interim Visits

If a subject experiences significant wound deterioration between scheduled study visits, the patient will be instructed to telephone the investigator immediately to arrange for an interim visit. Further treatment of the ulcer will be prescribed at the discretion of the investigator. Patients may be removed from the study if the situation warrants.

24 hour "paging system" Subjects will be instructed to call the Rosalind Franklin University Health Clinics if they have any questions or concerns. The Rosalind Franklin University Health Clinic has an after-hour answering service for patient emergencies where the on-call physician for the research group will be alerted of the situation. If a subject experiences any wound related irritation or complications, they will be urged to contact the clinics for an interim visit. Patients may be removed from the study if the situation warrants.

6.3 Potential Risks

Potential risks include wound or systemic infection and deterioration of wound. Any wound deterioration, or infection will be addressed with appropriate local and systemic therapy, as warranted. Evidence to support the diagnosis of wound deterioration, infection, abscess, or osteomyelitis would be considered an adverse event and recorded accordingly. Any cultured organism and antibiotic therapy will be recorded. Infection will be treated with aggressive debridement and appropriate systemic antibiotics as required until the infection has resolved. Microbiology confirmation will be recorded. Choice of antibiotic therapy is at the investigator's discretion. A wound culture will also be obtained (via curettage at the ulcer base, after wound debridement) if any signs of wound infection exist.

6.4 Removal of Patients from Therapy or Assessment

All patients are free to withdraw from participation in this study at any time, for any reason and without prejudice. The Investigator may terminate a patient from the study for administrative reasons, or in the Investigator's opinion, to protect the patient's best interest. If a patient is withdrawn before completing the study, the reason for withdrawal will be entered into patient's chart and reported accordingly. Whenever possible and reasonable, the evaluations which were to be conducted at the completion of the study should be performed at the time of premature discontinuation.

7.0 DATA HANDLING AND RECORDKEEPING

7.1 Data and Safety Monitoring Plan

We plan to use the NIDDK 'Data & Safety Monitoring (DSM) Guidelines for Clinical Trials'. [name] will evaluate the data on an ongoing basis and quarterly reports will be prepared to evaluate the progress of the trial (accuracy of data, verifying consent of subjects, and adherence to protocol schedule.). Clinical and patient data will be maintained, segregated and secured in locked filing cabinets only accessible to the Investigators. Patient records will be held as strictly confidential and names, or other identification, will not be used for publication or other purposes. All employees related to this grant request will be certified in accord with the NIH Human Participants Protection Education for Research Teams.

7.2 Patient Confidentiality

Upon entering the study each patient will be assigned a sequential number under which all study data will be stored. No personal identification information will be used. All information collected for this study will be secured in a locked office. Only the investigators and other members of study, independent ethics committees and inspectors from government regulatory agencies will be able to access patient medical records.

7.3 Ethics

This study will be conducted in compliance with the Declaration of Helsinki and its amendments, the International Conference on Harmonisation (ICH) principles of Good Clinical Practice (GCP) (including archiving of essential study documents) and the applicable regulations of the country in which the study is conducted.

A properly constituted, valid Institutional Review Board (IRB) or Independent Ethics Committee (IEC) must review and approve the protocol, the Investigator's informed consent form (ICF) and related patient information and recruitment materials before the start of the study.

It is the responsibility of the Investigator to ensure that written informed consent is obtained from the patient before any activity or procedure is undertaken that is not part of routine care.

8.0 STATISTICAL ANALYSIS

8.1 Sample Size Estimation:

Previous work done suggests that a small case series of 16 patients is adequate as a pilot trial. Accounting for a 20% potential fall out rate means that a total of 20 subjects should be enrolled into the study.

8.2 Data Analysis

Data analysis will include descriptive statistics and Chi-square and Fisher's exact tests for categorical variables. Continuous variable will be assessed using the Student t test, and where possible linear regression models. Outcomes variables will be compared with repeated measures of analysis of variance tests. Statistical significance will be accepted for p values <.05.

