3. STUDY END POINTS

3.1 Primary Endpoints

The primary endpoints are to explore clinical efficacy and include:

- 1. The extent and size of ulcers (summation of the products of the long x short axis for all ulcers measured in centimeters squared, plus ulcer depth) will be evaluated and photographs of ulcers taken during screening and on all clinic visits up to 20 weeks or when the ulcer is healed, whichever is sooner.
- 2. Leg rest pain score visual analogue scale (VAS) graded from 0 (pain free) to Grade 10 (maximum pain) during screening and on all clinic visits up to 20 weeks, or when the ulcer is healed, whichever is sooner.
- 3. Pain during Debridement score VAS graded from 0 (pain free) to Grade 10 (maximum pain) during on all clinical visits when debridement is performed for up to 20 weeks, sooner pending wound healing.
- 4. Subjects feedback regarding their debridement experience with micro water jet technology will be collected on all clinical visits when debridement is performed.
- 5. Incidence of wound infection.

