4. OVERALL STUDY DESIGN

4.1 Study Design

This is a prospective cohort, single-center, open-label study in subjects with chronic lower extremity wounds. The study will enroll up to 20 subjects. Subjects will undergo screening evaluations to determine eligibility to enroll in the study. All study subjects will receive micro water jet technology debridement as opposed to other debridement methods as part of their wound care treatment. The other aspects of subjects wound care protocol will remain unchanged. In the case of bilateral limb ulcers, or multiple ulcers, subjects will have the option to receive micro water jet debridement on one or all of the ulcers.

Clinical efficacy analyses will include assessment of changes in the extent and size of ulcers, percentage healing and rate of healing, leg rest pain score using VAS scale, pain experience during debridement using VAS scale, incidence of wound infection (See Section 3).

Safety assessments, including AE reporting, physical examination, vital sign measurements, concomitant medications will be performed at all clinical visits throughout the study.

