4.2 Study Duration

Up to 20 weeks, sooner pending wound healing as defined by 100% re-epithelialization.

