5.6 Subsequent visits

Patients will return to clinic every one to two weeks (+/- 2 days) as part of their regular wound care treatment plan for follow up assessment including wound evaluation and photograph. Wounds will be subsequently debrided using micro water jet technology if deemed appropriate by the investigators followed by a dry sterile dressing as previously described. Wound will be followed for a total of 20 weeks or when the wound has completely healed, as defined by 100% re-epithelialization.

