5.7 End of study visit

At the end of the 20-week evaluation, patients with open wounds will return to clinic on Day 112 (+/- 2 days) for the end of study visit. In cases of complete wound healing or patient withdraw, the end of study evaluation will take place at the patient's last day of study visit and will occur prior to Day 112. The following assessments will occur at the End of study visit:

- 1. Wound evaluation and photograph
- 2. VAS pain scale
- 3. Wound debridement (if applicable)

A wound dressing, if deemed necessary by the investigator will be applied.

5.8 Adjunctive Care:

All patients will receive standard adjunctive therapy for lower extremity ulcerations. Efforts will be made to control any edema by limb elevation, diuretic medication or compression hose, as indicated. Patients will be advised to stay off the affected foot as much as possible, and asked to avoid walking, except as absolutely necessary. Patients will be offered other assistive modalities at the time of enrollment (crutches, canes, and walkers) to enhance postural stability.

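### Ulcer size is recorded only until healing, yet section 8.2 gives its repeated-measures ANOVA no analysis times and no value for a healed patient, and the final visit has two conflicting dates

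*Combined protocol and SAP*

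**What the plan says.** Ulcer size is the first primary endpoint in section 3.1. It is defined as "summation of the products of the long x short axis for all ulcers measured in centimeters squared, plus ulcer depth" and is taken "on all clinic visits up to 20 weeks or when the ulcer is healed, whichever is sooner". Sections 4.2 and 5.6 stop follow-up at the same point: "Up to 20 weeks, sooner pending wound healing as defined by 100% re-epithelialization" and "Wound will be followed for a total of 20 weeks or when the wound has completely healed".

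The visit interval varies between patients: "Patients will return to clinic every one to two weeks (+/- 2 days) as part of their regular wound care treatment plan".

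Section 4.1 promises "assessment of changes in the extent and size of ulcers, percentage healing and rate of healing".

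For the analysis, section 8.2 says "Outcomes variables will be compared with repeated measures of analysis of variance tests". It also lists a t test for continuous variables and, where possible, linear regression. The Protocol Summary repeats this text. Neither place gives analysis times, visit windows, a missing-data rule, a value for a patient after complete healing, or an estimator for rate of healing.

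On the last assessment, section 5.7 says "patients with open wounds will return to clinic on Day 112 (+/- 2 days) for the end of study visit". It places the final evaluation of healed or withdrawn patients at their last visit, before that day. Section 6.4 asks for the end-of-study evaluations at premature discontinuation, where possible and reasonable.

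**The concern.** Whether a late ulcer size exists depends on the outcome itself: a patient whose ulcers have all closed supplies no later measurements. A classical repeated-measures ANOVA needs a complete set of values per patient, so it would drop everyone who healed before the last time point. A version that uses whatever is available would base late means on wounds still open plus those closing at that visit. Either way, the best responders are under-represented.

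The visit schedule adds a second difficulty. The eighth visit is week 8 for a patient seen weekly and week 16 for one seen every two weeks, so visit number is not a common time scale. The end of that scale is also unsettled.

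The study is a single-arm exploratory pilot with no decision rule, so no go/no-go decision is at risk. What is at stake is the wound-reduction estimate it reports, because methods that 8.2 permits can give different answers from the same data.

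**Working it through.** **Figures in the plan.** Section 8.1 takes 16 patients and 20% fall-out: 16/(1 − 0.20) = 20, which reproduces and is not in dispute. The closed form below uses n = 20.

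**Final time point.** 20 weeks × 7 = day 140 (sections 4.2, 5.6). 112/7 = week 16 (section 5.7). The difference is 28 days. A wound that closes in weeks 17 to 20 is within follow-up under 5.6, but 5.7 puts the final evaluation of healed patients before Day 112.

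**Who is affected.** While a patient with several ulcers still has one open, visits continue and a closed ulcer naturally adds nothing to the sum. The gap therefore concerns patients whose ulcers have all closed.

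**Size of the healing effect.** The documents give no healing or deterioration rate, so every input here is assumed:
- h = share healed by the end
- l = share healing at the last visit, who are still measured there
- r = mean % reduction in open wounds
- d = share removed for deterioration
- g = their % enlargement

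Formulas:
- All-patient mean = 100h + r(1 − h − d) − g·d
- Still-measured mean = [100l + r(1 − h − d)]/(1 − h − d + l)
- Gap = all-patient mean minus still-measured mean; positive means that reduction is understated

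Nobody removed (d = 0), l = h/4, r = 50:

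| Healed of 20 | All patients | Still measured | Gap (points) |
|---|---|---|---|
| 4 | 20 + 40 = 60.0% | (5 + 40)/0.85 = 52.9% (17 patients) | 7.1 |
| 8 | 40 + 30 = 70.0% | (10 + 30)/0.70 = 57.1% (14 patients) | 12.9 |
| 12 | 60 + 20 = 80.0% | (15 + 20)/0.55 = 63.6% (11 patients) | 16.4 |

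Sensitivity to r, for 4, 8 and 12 healed: 4.2, 7.7 and 9.8 points at r = 70; 9.9, 18.0 and 22.9 at r = 30.

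Sensitivity to l at r = 50: 10, 20 and 30 points if no healer closes at the last visit, which is the upper bound h(100 − r); 4.4, 7.5 and 8.6 if half do.

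**Effect of removals.** Section 6.2 allows removal if the situation warrants. Assume removed patients leave at 150% of baseline area (g = 50), with r = 50 and l = h/4. Gaps in points:

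| Healed of 20 | 1 removed | 2 removed | 3 removed | 4 removed |
|---|---|---|---|---|
| 4 | +1.9 | −3.3 | −8.6 | −13.8 |
| 8 | +7.3 | +1.7 | −4.1 | −10.0 |
| 12 | +10.0 | +3.3 | −3.8 | −11.4 |

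For 8 healed and 2 removed: 40 + 25 − 5 = 60.0% against (10 + 25)/0.60 = 58.3%. The last column assigns the whole 20% fall-out to deterioration, which is an extreme case.

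**The alternative within 8.2.** A paired comparison of baseline with the evaluation of section 5.7 or 6.4 uses 100% for healed patients, r for open wounds and −g for removed patients. That is the all-patient mean itself, so the gap is zero wherever those evaluations are obtained.

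**The case against.** The strongest reply is that the selection is conditional. A re-epithelialized wound has area zero by definition, and a sensible analyst might simply enter zero. Section 8.2 also offers a t test for continuous variables, which covers ulcer size as well as the ANOVA sentence does. Sections 5.7 and 6.4 supply the data for it. This stands. A reader might infer that the plan's late means are certain to be selected, or that the plan has no sound route to a wound-size estimate. The documents support neither: they do not say that healed patients are left out, and they permit a contrast that avoids the problem. What remains is that 8.2 neither states the zero rule nor makes that contrast the wound-size analysis.

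It is also fair that the magnitudes are invented inputs and that removals can change the sign. A reader might infer that the bias works against the device. That follows only for healing taken alone; section 6.2 leaves the number and condition of removed patients open.

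A reader might further infer that the plan needs a flexible mixed model. That is not shown. In simulated trials of 20 with assumed healing patterns and enlarging wounds removed (40 runs), a spline mixed model with healed wounds at zero had a root-mean-square error of 3.9 to 18.4 points. The mean of those still measured had 7.7 to 15.4.

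Finally, Day 112 against 20 weeks is a separate inconsistency. It is included because the final analysis time depends on it, not as evidence of the selection.

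**Conclusion.** The point holds in conditional form. If repeated-measures ANOVA is applied to the sizes as collected, early healers are dropped or late means rest mainly on open wounds, and healing by itself understates wound reduction. Under the main assumptions above, with nobody removed, the understatement is 7 to 16 points. This is an illustration and not an estimate for this trial. Once removals are allowed, the net direction is uncertain.

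The two parts differ in kind. The final time point is wrong as written, because Day 112 and 20 weeks cannot both be the end of follow-up. The analysis part is a cheap improvement: a usable method is already in 8.2, but it is not assigned to wound size and lacks the rule for healed patients.

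**What to change.** Amend section 8.2 and the matching Protocol Summary text:

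1. Count every ulcer included in the summed size as area 0 and depth 0 from the visit at which 100% re-epithelialization is recorded to the end of follow-up.
2. Make the primary wound-size analysis the within-patient change from baseline to the end-of-study evaluation in all treated patients, by paired t test or Wilcoxon signed-rank test, naming one. Healed patients count as 0; withdrawn or removed patients enter at their discontinuation value. Run any longitudinal model in actual weeks since baseline with healed = 0, as supportive only.
3. Report the proportion healed, and Kaplan-Meier time to 100% re-epithelialization as the rate of healing. Keep patients removed for deterioration as not healed to the end of follow-up, and censor other withdrawals at their last visit.
4. Reconcile Day 112 in section 5.7 with the 20-week follow-up in 5.6 and 4.2, so that one final time point is defined.

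Items 1 to 3 cost wording and a little analysis, with no new patients, visits or data; item 4 is a correction of the text. There are two downsides. The zero rule assumes that healed ulcers stay closed, which cannot be checked because follow-up stops at healing. The primary contrast uses the last value for patients who leave early, and it depends on the section 6.4 evaluation being obtained.

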2. STUDY OBJECTIVES

2.1 Primary Objective

The primary objective of this prospective cohort study is to assess the clinical effectiveness of micro water jet technology in the debridement and healing of chronic wounds in terms of wound size, depth/extent, and percent wound reduction and healing. Additional assessments will include evaluating changes in leg rest pain score using a visual analogue scale (VAS); incidence of infection, and pain during debridement via the VAS scale as well as patient feedback regarding their debridement experience with micro water jet technology.

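### The size endpoint can count ulcers the device never treated, and the end of follow-up has two dates; p<.05 over five unranked endpoints is a lesser problem

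*Combined protocol and SAP*

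**What the plan says.** **Which ulcers count.** The first primary endpoint in 3.1 is the "summation of the products of the long x short axis for all ulcers measured in centimeters squared, plus ulcer depth", assessed at screening and at every clinic visit until week 20 or healing. For patients with ulcers on both legs, or several ulcers, 4.1 says that "subjects will have the option to receive micro water jet debridement on one or all of the ulcers". No section names an index ulcer or limits the sum to treated ulcers.

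**When follow-up ends.** Sections 4.2 and 5.6 give 20 weeks, or earlier if the wound fully re-epithelializes. Section 5.7 describes a visit that closes the 20-week evaluation, dates it to Day 112 with a window of 2 days either side, and says that patients who heal or withdraw have their closing evaluation before Day 112.

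**How results are judged.** Section 3.1 opens with "The primary endpoints are to explore clinical efficacy and include" and lists five items without ranking: ulcer size, rest pain, pain during debridement, patient feedback and wound infection. Section 8.1 rests the sample size on the statement that "a small case series of 16 patients is adequate as a pilot trial". Section 8.2 names several tests, ties none to an endpoint or visit, and ends: "Outcomes variables will be compared with repeated measures of analysis of variance tests. Statistical significance will be accepted for p values <.05". Every subject receives the device (4.1).

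**The concern.** The primary objective in 2.1 is to assess the device "in terms of wound size, depth/extent, and percent wound reduction and healing". A size result that mixes treated and untreated ulcers does not answer that. It can hide a response in the treated ulcer, or credit the device with healing that happened elsewhere. Following the plan exactly produces this mixture in every patient who has several ulcers and does not have the device on all of them.

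The end date matters for the same outcomes. A wound still open on Day 112 that closes by Day 140 is unhealed under 5.7 and healed under 4.2 and 5.6. Final size and proportion healed therefore each have two possible meanings.

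The significance rule is a lesser matter. With five primaries, none of them leading, any one that falls below .05 could be reported as the efficacy finding. For infection and feedback it is unclear what would be tested. Infection is a proportion with no reference value, in patients whose ulcers show no gross infection at entry (5.3), and feedback has no scale. Even a clear change over time would not show efficacy against other debridement, because no group receives any.

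**Working it through.** **1. The plan's own figure.** Section 8.1 gives 16 patients and 20% fall-out: 16 / (1 − 0.20) = 20. The enrolled number reproduces. The 16 cannot be derived, because no effect size, standard deviation or power is stated.

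**2. Untreated ulcers in the sum.** Let s be the share of a patient's baseline summed area that lies in untreated ulcers, and let r_T and r_U be the fractional reductions in treated and untreated area. The reduction in the summed area is

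R = (1 − s) × r_T + s × r_U.

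The documents give no value for s, so 0.25, 0.50 and 0.75 are assumed.

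| Untreated share s | Treated heals, rest unchanged (r_T = 1, r_U = 0): R = 1 − s | Treated unchanged, rest heals (r_T = 0, r_U = 1): R = s |
|---|---|---|
| 0.25 | 75% | 25% |
| 0.50 | 50% | 50% |
| 0.75 | 25% | 75% |

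A milder case behaves the same way. If treated area halves and untreated area does not change, R = (1 − s) × 0.5, which is 37.5%, 25% or 12.5%. There is no distortion when s = 0 (single ulcer, or all treated) or when r_T = r_U.

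**3. End date.**
- 4.2 and 5.6: 20 × 7 = Day 140.
- 5.7: 112 / 7 = week 16.
- Gap: 140 − 112 = 28 days. The window in 5.7 runs only from Day 110 to Day 114, so it does not bridge the gap.

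**4. What a p-value could test, endpoint by endpoint.**
- Ulcer size and rest pain: 4.1 speaks of "assessment of changes in the extent and size of ulcers, percentage healing and rate of healing" and 2.1 of "changes in leg rest pain score". With repeated measures ANOVA, the implied null is no change over visits.
- Debridement pain: scored at each visit with debridement, so repeated measures ANOVA gives a null of equal means across visits.
- Infection and feedback: no comparison group, no reference value and, for feedback, no scale. No null is stated.

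**The case against.** **On the ulcers.** One could read the endpoint as meaning all study ulcers. No text says so, and the option in 4.1 is what makes the distinction necessary. It is fair that the problem affects only multi-ulcer patients who have fewer than all treated, that the plan does not say how many to expect, and that the percentages above simply follow from an assumed share.

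**On the end date.** Section 4.2 says up to 20 weeks, and 16 weeks fits inside that. But 5.6 gives 20 weeks as the total, and 5.7 itself calls the period a 20-week evaluation. The origin of the day count is not defined, yet nothing suggests that it starts four weeks late.

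**On significance testing.** The study declares itself exploratory and a pilot, so the absence of multiplicity control is a weak defect. That stands, and it is why this part is secondary.

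Four stronger readings are tempting and are not supported:
- A reader might infer a familywise error of 1 − 0.95^5 = 22.6%. That needs five independent tests. The plan assigns no test to any endpoint, two endpoints have no stated null, and independence is doubtful.
- A reader might infer that debridement pain has no null because there is no pre-device value. Comparison across visits supplies one.
- A reader might infer that healing was left out because 3.1 does not list it. It is named in 2.1 and 4.1 and defined in 4.2 and 5.6, so only the list needs aligning.
- A reader might infer that the walking aids offered at enrolment (5.8) explain any improvement. Nothing shows that they would be new to these patients.

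Lack of a comparator is the openly stated design. The error would lie only in reading a change from baseline as efficacy against other debridement.

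**Conclusion.** Two faults hold on the text, and no other section cures them. First, the size endpoint includes ulcers outside the device's reach. In an affected patient the reported reduction can be wrong by the full untreated share of baseline area in either direction: 25 to 75 percentage points over the assumed range, and nothing where all ulcers are treated or all change alike. With at most 20 patients, a few such cases could shift the summary. Second, follow-up ends on Day 112 or Day 140, 28 days apart, so final size and proportion healed have no single time point. The documents do not show which date is intended.

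The third part is secondary. A p<.05 rule over five unranked primaries fits poorly with a one-arm exploratory pilot, infection and feedback have no stated null, and a change over time cannot show superiority to other debridement. No error rate can be attached to it from the documents.

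**What to change.** 1. **Section 3.1.** Define the size endpoint as percent change per patient in summed area (long × short axis) of the ulcers selected for the device at the first debridement. Fix that set at baseline whatever is debrided later; 5.6 leaves later debridement to the investigators' judgement, so the set could otherwise shift after outcomes are seen. Tabulate untreated ulcers and depth separately.
2. **Sections 4.2, 5.6 and 5.7.** Reconcile 20 weeks with Day 112, including the statement in 5.7 about healed patients, so that the final visit has one meaning.
3. **Section 8.2.** Make that percent change the lead endpoint and report it with a 95% CI, for example an exact order-statistic interval for the median, which does not need symmetric changes. Report complete healing, as already defined, as a proportion of enrolled patients with an exact 95% CI and the number of withdrawals shown. Report the other endpoints descriptively. State that a change from baseline is not evidence of efficacy versus other debridement.

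The cost is wording, plus tabulating area by ulcer from axes already measured. The sample size stays at 20. The downside is that fewer results can be called significant.
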